2.2. Sample Size Considerations

Because this is an extension of study MVT-601-3003, the sample size of this study was based on approximately the number of patients who completed a pivotal study (n = 780 patients in total), and who participated in the LTE study (n = 600 patients in total assuming about 20% dropout rate at 6 months from the pivotal studies). Assuming the proportion of responders at Week 52 in MVT-601-3003 LTE study is 60%, it was estimated that approximately 360 patients were to be randomized into this study.

With 360 patients, the study would have at least 90% power to detect a difference of 20% or greater between relugolix+ E2/NETA group and placebo group for the primary endpoint. The following assumptions were used to determine the sample size for this study:

- 2-sided type I error rate: 0.05
- Randomization: 1:1
- Responder rate for placebo group: 40%
- Responder rate for relugolix + E2/NETA group: 60%
- Dropout rate: 20%

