4. GENERAL CONSIDERATIONS FOR DATA ANALYSES AND HANDLING OF MISSING DATA

4.1. Data Presentation Conventions

All statistical analyses will be conducted using SAS[®] Version 9.2 or higher.

All confidence intervals (CIs) will be reported as two-sided unless otherwise stated.

Where appropriate, variables will be summarized descriptively by study visit. For the categorical variables, the count and proportions of each possible value will be tabulated by treatment group. For continuous variables, the number of patients with non-missing values, mean, median, standard deviation (SD), minimum, and maximum values will be tabulated.

Unless otherwise specified, the following conventions will be applied to all analyses:

- Mean and median values will be formatted to one more decimal place than the measured value. Standard deviation values will be formatted to two more decimal places than the measured value. Minimum and maximum values will be presented to the same number of decimal places as the measured value. If the measured value is large (eg, > 100), fewer decimal places may be displayed.
- Percentages will be rounded to one decimal place;
- p-values will be rounded to four decimal places. p-values < 0.0001 will be presented as “< 0.0001” and p-values > 0.9999 will be presented as “> 0.9999”;
- 1 month = 30.4375 days. Month is calculated as (days/30.4375) rounded to one decimal place;
- 1 year = 365.25 days. Year is calculated as (days/365.25) rounded to one decimal place;
- Age will be calculated using the date of randomization. If only year of birth is collected, 1 July of the year of birth will be used to calculate age.
- 1 pound = 0.454 kg;
- 1 inch = 2.54 cm;
- Missing efficacy or safety data will not be imputed, unless otherwise specified;
- For laboratory results above or below sensitivity limits displayed as “<” or “>,” a quantification threshold, 0.000000001, will be subtracted or added, respectively, to the threshold to derive a numeric result for analyses;
- For MBL volume reported as below the limit of quantification (eg, MBL below Quantification Level < 5.0 mL or < 2.5 mL), 0.000000001 will be subtracted from the reported quantification threshold for the visit to derive a numeric result for analyses;
- For safety analyses, calculation of percentages will be calculated on the basis of the number of patients in the analysis population in each treatment group;

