9.1. Adverse Events

Adverse events will be collected from the time of the first dose of randomized withdrawal study drug through the safety follow up visit approximately 30 days after the last dose of randomized withdrawal study drug (if no retreatment was initiated) or approximately 30 days after the last dose of retreatment drug (if the retreatment was initiated), or the date of initiation of another investigational agent or hormonal therapy (eg, elagolix, acotol) or surgical intervention (eg, uterine artery embolization), whichever occurs first. Serious adverse events reported to the investigator after the safety reporting period should be reported to the sponsor if the investigator assesses the event as related to study drug.

The severity of all treatment-emergent adverse events will be evaluated by the investigator based on the National Cancer Institute's Common Terminology Criteria for Adverse Events (CTCAE), v.5.0 dated 27 Nov 2017, and will be coded to preferred term and system organ class using MedDRA 24.0 or higher.

A treatment-emergent adverse event for cumulative treatment period (including the randomized treatment and the retreatment periods) is defined as any adverse event that onsets or worsens after administration of the first dose of randomized withdrawal study drug.

For patients who stayed on the randomized treatment till end of the study, a treatment-emergent adverse event for the randomized treatment period is defined as any adverse event that onsets or worsens after administration of the first dose of randomized withdrawal study drug. For patients who had the retreatment drug initiated, any adverse event that onsets or worsens after administration of the first dose of randomized withdrawal study drug and prior to the initiation of the retreatment drug is defined as treatment-emergent adverse event for the randomized treatment period.

For patients who started the retreatment drug, a treatment-emergent adverse event for the retreatment period is defined as any adverse event that onsets after the initiation of retreatment drug.

Adverse event summaries will be based on treatment-emergent adverse events in the randomized withdrawal study, unless otherwise specified. The summaries will mainly be done for the cumulative treatment period. Some selected summaries may be provided for the randomized withdraw period and the retreatment period separately. All adverse events will be listed in by-patient listings.

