The following tabular summaries that include the number and percentage of patients will be provided for the cumulative treatment period:

- Overview of adverse events;
- All adverse events;
 - By SOC and PT;

- By decreasing frequency of PT;
- By SOC, PT, and maximum severity;
- Drug-related per investigator by SOC and PT;
- By time to onset, SOC and PT;
- Grade 3 or higher adverse events;
 - By SOC and PT;
 - By decreasing frequency of PT;
 - Drug-related per investigator by SOC and PT;
- Adverse events leading to study drug withdrawal;
 - By SOC and PT;
 - By decreasing frequency of PT;
- Adverse events leading to dose interruption;
 - By SOC and PT;
 - By decreasing frequency of PT;
- Adverse events resulting in fatal outcome;
 - By decreasing frequency of PT;
- Serious adverse events;
 - By SOC and PT;
 - By decreasing frequency of PT;
 - By SOC, PT, and maximum severity;
 - By SOC, PT, and relationship to study drug;
- Adverse events of special interest or clinical interest (ALT or AST $\geq 3 \times$ ULN);
 - By SOC, PT, and maximum severity;
 - By decreasing frequency of PT.
- Adverse events with first onset during the randomized withdrawal study;
 - By SOC and PT;
 - By decreasing frequency of PT.

Additionally, adverse event categories defined in [Table 15](#) will be summarized by decreasing frequency of PT for the cumulative treatment period.

The following tabular summaries that include the number and percentage of patients will be provided for the retreatment period:

- Overview of adverse events;

- All adverse events;
 - By SOC and PT;
 - By decreasing frequency of PT;
 - By time to onset, SOC and PT;
- Grade 3 or higher adverse events;
 - By SOC and PT;
 - By decreasing frequency of PT;
- Adverse events leading to study drug withdrawal;
 - By SOC and PT;
 - By decreasing frequency of PT;
- Serious adverse events;
 - By SOC and PT;
 - By decreasing frequency of PT;
- Adverse events of special clinical interest (ALT or AST $\geq 3 \times$ ULN);
 - By decreasing frequency of PT.

The adverse events which were ongoing at the time of randomization of the randomized withdrawal study will be summarized as specified below. Such adverse events were collected during the pivotal study and LTE study and they are considered pre-existing conditions for the randomized withdrawal study.

- All adverse events;
 - By SOC and PT;
 - By decreasing frequency of PT;
- Grade 3 or higher adverse events;
 - By SOC and PT;
 - By decreasing frequency of PT;

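### The period-specific adverse event tables use crude percentages despite unequal time at risk, and the randomized-period event definition omits women who stop early without retreatment

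*SAP*

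**What the plan says.** **What ends randomized drug.** A woman whose blood loss returns to 80 mL or more is offered open-label relugolix + E2/NETA at her next menses (SAP 4.3.2). Her last randomized dose is taken the day before the retreatment visit (Protocol 6.2). A relapser who declines retreatment leaves through an Early Termination visit (SAP 2.1).

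**Which periods are tabulated.** SAP 9.1 makes the cumulative period (randomized plus retreatment) the main one. Separate randomized-period summaries are optional and none is listed. Retreatment-period tables are a commitment: "The following tabular summaries that include the number and percentage of patients will be provided for the retreatment period".

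**The measure.** The cumulative tables also give number and percentage of patients. SAP 4.1 fixes the denominator: "For safety analyses, calculation of percentages will be calculated on the basis of the number of patients in the analysis population in each treatment group". A tabulation by time to onset is listed under the same number-and-percentage heading. SAP 6 summarizes treatment duration separately. SAP 9 contains no person-time rate.

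**The randomized-period event.** SAP 9.1 defines it for two groups. One begins: "For patients who stayed on the randomized treatment till end of the study". The other is women who started retreatment. The cumulative-period definition has no such restriction.

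**The concern.** A woman's chance of having at least one event rises with the time she is watched. Relapse ends randomized treatment, and the plan expects more relapse on placebo, so the placebo arm is observed for less time on randomized drug. Retreatment can begin at almost any point in the year, so its length varies widely between women. A percentage with a fixed patient denominator ignores both facts.

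The cumulative tables do not fill the gap. Nominal follow-up is equal there, but a retreated placebo woman stays in the placebo column: SAP 4.2.3 reclassifies a patient as relugolix only for relugolix taken during the randomized period. Relugolix exposure inside the placebo column tends to pull the arms together. The uncontaminated comparison is the randomized period. For that period the summary is optional, the measure depends on exposure, and the event definition is incomplete.

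The SAP already treats this cut-off as a problem for efficacy. It uses Kaplan-Meier estimates for relapse (SAP 7.3.1) and drops mixed models in the randomized period because censoring at retreatment is informative (SAP 7.1.2).

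**Working it through.** **Inputs from SAP 2.2.** Week 76 responder rates of 40% (placebo) and 60% (relugolix + E2/NETA), 360 patients randomized 1:1, "2-sided type I error rate: 0.05", dropout 20%.

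**The plan's own figure.** With 180 × 0.8 = 144 per arm and a pooled-variance test, power = Φ[(0.2√144 − 1.96√0.5)/√0.48] = Φ(1.46) = 92.8%. The stated power of at least 90% reproduces. The documents give no adverse event rate, so nothing on the safety point itself can be reproduced.

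**Assumptions not in the documents.** Constant relapse hazard; no dropout; a lag L of 0, 4 or 8 weeks from relapse to retreatment; the same true event rate in both arms, 0.5 per patient-year (λ = 0.5/52.18 per week).

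**Hazards.** h = −ln(S24)/24: placebo −ln(0.4)/24 = 0.0382 per week; relugolix −ln(0.6)/24 = 0.0213 per week.

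**Mean weeks on randomized drug, out of 52.** L + [1 − exp(−h(52 − L))]/h.

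**Crude percentage with an event.** 1 − e^(−λL) + e^(−λL) × [λ/(λ + h)] × [1 − exp(−(λ + h)(52 − L))].

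| Lag (weeks) | Mean weeks, relugolix vs placebo | Ratio | Crude %, relugolix vs placebo | False ratio |
|---|---|---|---|---|
| 0 | 31.4 vs 22.6 | 1.39 | 24.8 vs 18.4 | 1.35 |
| 4 | 34.1 vs 26.0 | 1.31 | 26.8 vs 21.1 | 1.27 |
| 8 | 36.6 vs 29.3 | 1.25 | 28.7 vs 23.7 | 1.21 |

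An exposure-adjusted rate would give 0.5 against 0.5, a ratio of 1.00, in every row.

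**Sensitivity.** For event rates from 0.1 to 1.0 per patient-year, the false ratio runs from 1.38 to 1.31 with no lag and from 1.24 to 1.18 with an 8-week lag. With 20% dropout by Week 24 in both arms and a rate of 0.5, it is 1.31 (no lag) to 1.18 (8 weeks).

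**Cumulative period.** With full follow-up each arm shows 1 − exp(−0.5 × 52/52.18) = 39.2%, so there is no exposure artefact. If all relapsers accept retreatment, the placebo arm's open-label share is (52 − 22.6)/52 = 57% with no lag, (52 − 26.0)/52 = 50% at 4 weeks and (52 − 29.3)/52 = 44% at 8 weeks.

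**Definition.** A woman who stops randomized drug for an adverse event, or who relapses and declines retreatment, neither stayed on randomized treatment to the end nor started retreatment. SAP 5.1 expects such women, since it counts premature discontinuations. Protocol 9.5 gives one treatment-emergent window for everyone, to about 30 days after the last dose, but does not divide events by period.

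**The case against.** The strongest reply is about scope. The committed between-arm tables are cumulative, with nominally equal follow-up, and the plan does not promise a randomized-period table. This stands, and it limits the point. A reader might infer that the trial's adverse event reporting as a whole is biased against relugolix; the documents do not support that. Nor does the SAP plan to compare retreatment-period percentages with randomized relugolix.

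The size is also easy to overstate. Drug continues past relapse until the next menses, so a zero lag is the extreme case. A ratio near 1.7 needs an 80% relugolix rate, which appears nowhere in the documents. It would be equally wrong to say that relugolix women mostly stay on randomized drug: at the plan's 60% and a constant hazard, 0.6^(52/24) = 33% are relapse-free at 52 weeks. Events clustered soon after randomization, before many women have left either arm, would give nearly undistorted percentages.

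On the definition, the wording about staying to the end could be read as each non-retreated woman's own end of study. A reader might infer that events ending treatment are lost. They are not: the cumulative definition covers them, and events leading to withdrawal are tabulated on it. What remains is a literal gap in the randomized-period wording.

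The onset-time tables and duration summaries reveal unequal exposure but do not adjust for it.

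**Conclusion.** The point holds in limited form. The cumulative tables have nominally equal follow-up but a mixed placebo column, with 44% to 57% of its time on open-label relugolix under the 40% placebo rate and full acceptance of retreatment. The randomized period is the only uncontaminated placebo-controlled contrast. A crude percentage there would show a false relugolix-to-placebo ratio of about 1.2 to 1.35 when the true rates are equal. That range rests on the SAP's 40% and 60%, a constant relapse hazard, no dropout, a 0 to 8 week lag and 0.5 events per patient-year; only the two responder rates come from the documents. The mandatory retreatment-period percentages likewise pool women with very different exposure. The gap in the event definition is real on a literal reading but touches only randomized-period summaries. This is a cheap improvement to safety reporting; it does not affect the primary efficacy analysis.

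**What to change.** Amend SAP 9.1 in three ways.

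1. Commit to a randomized-period adverse event summary by arm.
2. Beside the percentages, report first events per 100 patient-years for the randomized period, with the arm difference and 95% CI, and for the retreatment period. Count each woman's time at risk over the same window as the events, ending at her first event.
3. Define the randomized-period treatment-emergent event once, for all women: onset or worsening from the first randomized dose to the earliest of the first retreatment dose, about 30 days after the last randomized dose, or the other stops already in Protocol 9.5 and SAP 9.1 (another investigational agent, hormonal therapy or surgical intervention).

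The cost is a few sentences and some extra table columns. The dose dates are already defined in SAP 4.3.1 and 4.3.2, so no new data are needed. Person-time rates remove the distortion fully only if event risk is roughly constant over time, so the percentages and onset-time tables should stay alongside them.

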4.2.3. Safety Population

The Safety population consists of all patients who were randomized and took at least one dose of study treatment. All safety analyses will be performed using the safety population, unless otherwise specified. Safety data will be analyzed by treatment group according to the actual treatment received (not the randomized treatment). Any patient who received at least one dose of relugolix during the randomized treatment period will be considered as a relugolix patient.

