4.2.4. Retreatment Population

The Retreatment population consists of those patients in the mITT Population who started the retreatment. Selected efficacy and safety data will be analyzed using the retreatment population.

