5.5. Prior Medications and Concomitant Medications

Prior medications and concomitant medications taken during this Randomized Withdrawal Study treatment period will be summarized for all patients in the Safety population by randomized treatment group. In addition, concomitant medications taken during the retreatment period will also be summarized for Safety Population by their randomized treatment group. Medications are considered concomitant for randomized treatment period if exposure occurs during the randomized treatment period. Medications are considered concomitant for retreatment period if exposure occurs during the retreatment period. Medications are considered prior if exposure started prior to the date of first dose of randomized withdrawal study drug.

The number and percentage of patients who took at least one dose of a prior or concomitant medication will be summarized by randomized treatment group and overall using the World Health Organization (WHO) Drug Dictionary and summarized according to the Anatomical Therapeutic Chemical (ATC) Classification System and generic medication name. A patient who has been administered several medications with the same preferred medication name will be counted only once for that preferred medication name.

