9. SAFETY ANALYSES

Unless otherwise specified, safety analyses will be conducted using the safety population according to the actual treatment received by the patients in this randomized withdrawal study.

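### Retreatment-period medication percentages are set on the whole Safety population, and the retreatment adverse event tables fall there by default, so the percentages are diluted, and unequally between arms

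*SAP*

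**What the plan says.** Four parts of the SAP bear on the denominator.

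- **Default population.** Section 9 opens: "Unless otherwise specified, safety analyses will be conducted using the safety population according to the actual treatment received by the patients". Section 4.2.3 defines that population: "The Safety population consists of all patients who were randomized and took at least one dose of study treatment". Whether a woman was ever retreated plays no part in it.
- **Percentage rule.** For safety analyses, Section 4.1 says that "calculation of percentages will be calculated on the basis of the number of patients in the analysis population in each treatment group".
- **Retreatment-period outputs.** Section 9.1 introduces its retreatment adverse event tables with "The following tabular summaries that include the number and percentage of patients will be provided for the retreatment period" and names no population. The same section defines a retreatment-period treatment-emergent event only for women who started the retreatment drug. Section 5.5 is explicit on medications: "In addition, concomitant medications taken during the retreatment period will also be summarized for Safety Population by their randomized treatment group".
- **Retreatment population.** Section 4.2.4 says: "The Retreatment population consists of those patients in the mITT Population who started the retreatment". It adds: "Selected efficacy and safety data will be analyzed using the retreatment population". It does not say which data are selected.

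**The concern.** A retreatment-period event, or a medication taken during retreatment, can be recorded only in a woman who restarted the drug. A denominator of every dosed woman also counts those who never relapsed, declined retreatment or left early. None of them can enter the numerator.

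Two consequences follow. First, the printed percentage is lower than the incidence among women exposed to retreatment. Second, the shrinkage is greater in the arm with fewer relapses. All retreated women take the same open-label relugolix + E2/NETA, so equal true incidence would appear as a difference between the randomized columns that reflects only how many women were retreated. These are the only tables in SAP 9.1 confined to the retreatment period. The cumulative tables mix the two periods.

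**Working it through.** **1. Which denominator the text gives.** For medications, Section 5.5 names the Safety population, so nothing has to be inferred about the population. For adverse events, Section 9.1 names none. The Section 9 default and the Section 4.1 rule together give all dosed women in the arm, unless the clause on selected data in Section 4.2.4 is read to cover these tables.

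**2. Planning inputs (SAP 2.2).** 360 women randomized 1:1, so 180 per arm; responder rates 40% on placebo and 60% on relugolix + E2/NETA; dropout 20%; 2-sided alpha 0.05. The plan's stated power is at least 90%. Check: evaluable per arm = 180 × 0.8 = 144. The standard error under the null is √(2 × 0.5 × 0.5 / 144) = 0.0589, and under the alternative √((0.6 × 0.4 + 0.4 × 0.6) / 144) = 0.0577. Then z = (0.20 − 1.96 × 0.0589) / 0.0577 ≈ 1.46, which is power of about 92.8%. The stated figure reproduces, so these rates are a fair basis for an illustration.

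**3. Formula.** Let f = women retreated / women in the Safety population of that arm. Printed percentage = true percentage among retreated women × f. Relative dilution = 1 − f.

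**4. Scenarios.** The documents state no f. Each row below assumes that every non-responder still in the study is retreated.

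| Assumption | Placebo f | Dilution | Relugolix f | Dilution | True 10% prints as (placebo / relugolix) |
|---|---|---|---|---|---|
| No dropout: f = 1 − responder rate | 0.60 (108/180) | 40% | 0.40 (72/180) | 60% | 6.0% / 4.0% |
| 20% dropout independent of relapse: f = 0.8 × (1 − responder rate) | 0.48 | 52% | 0.32 | 68% | 4.8% / 3.2% |
| 20% dropouts counted among non-responders, never retreated: f = (1 − responder rate) − 0.20 | 0.40 | 60% | 0.20 | 80% | 4.0% / 2.0% |

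Pooled over arms, f is 0.50, 0.40 and 0.30. Over a wider assumed range, f = 0.90 gives 10% dilution and f = 0.10 gives 90%.

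**5. Apparent arm difference.** With equal true incidence, the ratio of the printed percentages (placebo to relugolix) is the ratio of the f values: 0.60/0.40 = 1.5, 0.48/0.32 = 1.5, and 0.40/0.20 = 2.0.

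**6. Denominator of retreated women.** There f = 1 by construction. The dilution is zero in both arms and the artificial ratio disappears.

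**The case against.** The strongest reply is that the adverse event tables may already belong to the Retreatment population. Section 4.2.4 reserves selected safety data for it. Section 9.1 also speaks of selected summaries when it mentions separate retreatment-period output, and it defines the events only for women who started the drug. This stands as a reason to call the adverse event denominator ambiguous. It does not remove the point, because the default yields only where something else is specified and no table is. Section 5.5 shows that the authors did place one retreatment-period summary on the Safety population. A programmer could follow either reading.

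A second reply is that Section 5.5 lies outside the safety chapter, while the Section 4.1 rule is worded for safety analyses. That is fair as to the rule, but Section 5.5 names the population itself and reports numbers and percentages of patients.

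A third reply is that the harm is limited, and this largely stands. Section 4.2 requires the size of each analysis population to be reported by group, and the tables print counts, so a careful reader can recover the right rate by one division. The tables are descriptive and carry no test.

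A reader might go further and infer any of the following. The documents do not support them.

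- That adverse event rates on retreatment are definitely understated by 40% to 60%. This needs the Week 76 planning rates, full uptake and no dropout. Retreatment can also start after Week 76, so f could be higher or lower.
- That most women are never retreated. Without dropout, the planning rates imply 60% retreated on placebo and 50% pooled.
- That the dilution always exceeds 10%. At f = 0.90 it is exactly 10%.
- That retreatment exposure summaries (SAP 6) are diluted in the same way. They are mainly dose, tablet counts and duration, and a woman never retreated has no retreatment duration to average in.
- That safety on restarting is a stated purpose of the design. Protocol 4.2 speaks of the effectiveness of retreatment.

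**Conclusion.** The point holds in a limited form. For concomitant medications the SAP names a population that includes women who cannot contribute. For adverse events the default leads to the same place, subject to an undefined clause that might override it. Whenever fewer than all women are retreated, percentages on the Safety population are diluted by 1 − f, and by different amounts in the two arms whenever the retreated fractions differ. The figures of 40% and 60%, or 52% and 68% with independent dropout, are illustrations from the planning assumptions. They are not estimates of what the trial will show. Efficacy inference and the cumulative safety tables are unaffected. The matter is worth settling in the SAP before database lock because the two candidate denominators can differ by a factor of about two.

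**What to change.** In SAP 9.1 and 5.5, state that retreatment-period adverse event and concomitant medication percentages use the Retreatment population, with N equal to the women in each randomized group who took at least one retreatment dose. Add an overall column, since all these women take the same open-label drug. In Section 4.2.4, replace the reference to selected data with a list of the outputs that use this population. Because time on retreatment varies, exposure-adjusted rates could be added, but the correction does not depend on them.

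The cost is a few lines of wording and a population flag that the SAP already defines. The only downside is smaller denominators, and so less precise percentages, in descriptive tables.
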